6. ANALYSES AND SUMMARIES

Refer to Section 4 for definitions of analysis sets and Section 5.1.2.1 for general methodology.

6.1. Primary Endpoints

6.1.1. DLT for Phase 1b

6.1.1.1. Primary Analysis

DLT rate is calculated as the number of DLT-evaluable participants with DLTs in the DLT-evaluation period divided by the number of DLT-evaluable participants in the DLT-observation period.

6.1.2. Phase 2

6.1.2.1. Sub-Study A - Durable Objective Response

6.1.2.1.1. Primary analysis

Durable ORR is calculated as the proportion of participants in the full analysis population with durable OR along with a 2-sided 95% CI for durable ORR using the Clopper-Pearson method. Participants who do not have a post-baseline tumor assessment due to early progression of disease, who receive anti-cancer therapies other than the study treatments prior to reaching a CR or PR for 10 months, or who die, have PD, or stop tumor assessments for any reason prior to reaching a CR or PR for 10 months will be counted as non-responders in the assessment of Durable OR. Each participant will have a durable objective response status (0: no durable OR; 1: durable OR).

Refer to Section 6.2.2 for assessment of response.

6.1.2.2. Sub-Study B - Objective Response

6.1.2.2.1. Primary analysis

ORR is calculated as the proportion of participants in FAS with confirmed OR along with a 2-sided 95% CI for ORR using the Clopper-Pearson method. Participants who do not have a post-baseline tumor assessment due to early progression of disease, who receive anti-cancer therapies other than the study treatments prior to reaching a CR or PR, or who die, have PD, or stop tumor assessments for any reason prior to reaching a CR or PR will be counted as non-responders in the assessment of OR. Each participant will have an objective response status (0: no OR; 1: OR).

Refer to Section 6.2.2 for assessment of response.

ORR will be presented by treatment arm B1, B2, B3 and overall where participants will be assigned to a relevant arm using PD-L1 expression determined by local assessment (refer to Section 3.4.1). ORR summary by PD-L1 expression using central assessment will also be presented.

6.2. Secondary Endpoint(s)

6.2.1. Safety endpoints

Refer to Section 6.6.

6.2.2. Efficacy endpoints

The following analyses will be based on the full analysis set by sub-study and treatment group. Assessment of response will be made using RECIST v1.1. Tumor-related endpoints will be analyzed based on investigator assessment.

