Once the RP2D of the triplet is defined, the Phase 2 part of the study may be initiated. Participants will be allocated to 1 of 3 treatment arms based on lines of prior therapy and PD-L1 TPS. For participants with previously untreated NSCLC, competitor data for PDx/TIGIT doublet combinations suggest that clinical activity may be enriched in the subgroup of participants with PD-L1 TPS $\geq 50\%$ as compared to those with PD-L1 TPS 1-49%. Therefore, participants will be enrolled into 2 separate treatment arms based on PD-L1 expression to allow for estimation of clinical activity in each subgroup:

- Treatment Arm B1 (n=20): treatment-naïve participants with low PD-L1 (levels 1-49%);
- Treatment Arm B2 (n=20): treatment-naïve participants with high PD-L1 (levels $\geq 50\%$).

Given the existing data and high unmet need, a 3rd group of participants who have received prior checkpoint treatment is planned:

- Treatment Arm B3 (n=20): participants whose disease has progressed on prior PD-1/PD-L1 therapy and who have PD-L1 TPS $\geq 1\%$.

Phase 2 will enroll a total of approximately 60 participants and will evaluate the anti-tumor activity and further evaluate the safety of the triplet combination of sasanlimab + axitinib + SEA-TGT.

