3.4. Baseline Variables

3.4.1. Study drug, study treatment and baseline definitions

In this study, ‘**study drug**’ refers to sasanlimab or encorafenib or binimetinib for Sub-Study A, sasanlimab or axitinib or SEA-TGT for Sub-Study B, and ‘**study treatment**’ (or ‘**treatment group**’) refers to:

- Phase 1b Sub-Study A Dose Level 0: sasanlimab 300mg + encorafenib 300mg + binimetinib 45mg
- Phase 1b Sub-Study A Dose Level 1: sasanlimab 300mg + encorafenib 450mg + binimetinib 45mg
- Phase 1b Sub-Study A Dose Level -1: (sasanlimab 300mg + encorafenib 300mg + binimetinib 30mg
- Phase 2 Sub-Study A: To be determined from Phase 1b
- Phase 1b Sub-Study B: sasanlimab **CCI** + axitinib 5 mg BID
- Phase 1b Sub-Study B: sasanlimab **CCI** + axitinib 3 mg BID
- Phase 1b Sub-Study B: sasanlimab **CCI** + axitinib 5 mg BID + SEA- TGT DL0
- Phase 1b Sub-Study B: sasanlimab **CCI** + axitinib 5 mg BID + SEA- TGT DL1
- Phase 1b Sub-Study B: sasanlimab **CCI** + axitinib 5 mg BID + SEA- TGT DL-1

- Phase 1b Sub-Study B: sasanlimab **CCI** + axitinib 3 mg BID + SEA- TGT DL0
- Phase 1b Sub-Study B: sasanlimab **CCI** + axitinib 3 mg BID + SEA- TGT DL1
- Phase 1b Sub-Study B: sasanlimab **CCI** + axitinib 3 mg BID + SEA- TGT DL-1
- Phase 2 Sub-Study B: To be determined from Phase 1b

Phase 2 Sub-Study B participants will be assigned in the following 3 study arms:

- Arm B1: Participants who report (i) no prior advanced or metastatic therapy and (ii) locally assessed PD-L1 TPS \geq 50%
- Arm B2: Participants who report (i) no prior advanced or metastatic therapy and (ii) locally assessed PD-L1 TPS \geq 1% and TPS $<$ 50%
- Arm B2: Participants who report (i) prior advanced or metastatic therapy and (ii) locally assessed PD-L1 TPS \geq 1%

Start and end dates of study treatment:

The date/time of first dose of study treatment in a combination group is the earliest date/time of the first non-zero dose date/time for the study drugs in the combination.

The date/time of last dose of study treatment in a combination group is the latest date/time of the last non-zero dose date/time for the study drugs in the combination.

Definition of baseline:

Definition of baseline for efficacy and PRO analyses and for safety analyses

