5.2. General Methods

As described in Section 3.4, in this study ‘**treatment group**’ refers to:

- Phase 1b Sub-Study A Dose Level 0: sasanlimab 300mg + encorafenib 300mg + binimetinib 45mg

- Phase 1b Sub-Study A Dose Level 1: sasanlimab 300mg + encorafenib 450mg + binimetinib 45mg
- Phase 1b Sub-Study A Dose Level -1: sasanlimab 300mg + encorafenib 300mg + binimetinib 30mg
- Phase 2 Sub-Study A: To be determined from Phase 1b
- Phase 1b Sub-Study B: sasanlimab CCI + axitinib 5 mg BID
- Phase 1b Sub-Study B: sasanlimab CCI + axitinib 3 mg BID
- Phase 1b Sub-Study B: sasanlimab CCI + axitinib 5 mg BID + SEA- TGT DL0
- Phase 1b Sub-Study B: sasanlimab CCI + axitinib 5 mg BID + SEA- TGT DL1
- Phase 1b Sub-Study B: sasanlimab CCI + axitinib 5 mg BID + SEA- TGT DL-1
- Phase 1b Sub-Study B: sasanlimab CCI + axitinib 3 mg BID + SEA- TGT DL0
- Phase 1b Sub-Study B: sasanlimab CCI + axitinib 3 mg BID + SEA- TGT DL1
- Phase 1b Sub-Study B: sasanlimab CCI + axitinib 3 mg BID + SEA- TGT DL-1
- Phase 2 Sub-Study B: To be determined from Phase 1b

The following will be provided by sub-study and corresponding treatment groups.

Baseline characteristics, disposition, and efficacy data will be summarized based on the FAS by sub-study and treatment group.

DLTs will be summarized based on the DLT-evaluable set by sub-study and treatment group including data from Phase 1b only.

Other safety data, exposure data, concomitant medications and non-drug treatments will be summarized based on the safety analysis set by sub-study and treatment group.

PK data will be summarized based on the PK analysis set by sub-study and treatment group.

Biomarker data will be summarized based on the biomarker analysis set by sub-study and treatment group.

Immunogenicity data will be summarized based on the immunogenicity analysis set by sub-study and by treatment group, if data permit.

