6.4. Subset Analyses

Applicable to Phase 2 only.

Durable OR (Sub-Study A only) and OR will be summarized in the following subsets within each treatment group:

- Pooled Geographical Region
 - North America
 - Europe
 - Asia
 - Rest of World (ROW)
- Age
 - Age < 65 years
 - Age ≥ 65 years
- Gender
 - Male
 - Female
- Race
 - White
 - Asian
 - Black or African American
 - Other
- ECOG PS
 - 0
 - ≥1

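### Read literally, the SAP's 'treatment group' definition puts all of Sub-Study B Phase 2 into one group for the secondary efficacy outputs, so by-arm presentation needs to be stated

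*SAP*

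**What the plan says.** Sections 3.4.1 and 5.2 list the treatment groups. Phase 1b is split by dose level. Sub-Study B Phase 2 is one line in both lists: "Phase 2 Sub-Study B: To be determined from Phase 1b". In Section 3.4.1 the three populations come after that list under a different term: "Phase 2 Sub-Study B participants will be assigned in the following 3 study arms". Section 5.2 repeats the list without the arms.

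The analysis rules use the listed term. Section 5.2 says "Baseline characteristics, disposition, and efficacy data will be summarized based on the FAS by sub-study and treatment group", and Section 6.2.2 says "The following analyses will be based on the full analysis set by sub-study and treatment group". The DR, PFS and OS subsections and the waterfall plot repeat the treatment-group wording. The TTR subsection names no grouping, so the opening rule of Section 6.2.2 applies to it.

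Arms are named for the primary endpoint only. Section 6.1.2.2.1 says "ORR will be presented by treatment arm B1, B2, B3 and overall".

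The design text in Section 2.2.2 says "Participants will be allocated to 1 of 3 treatment arms based on lines of prior therapy and PD-L1 TPS". For the treatment-naive populations it explains that "participants will be enrolled into 2 separate treatment arms based on PD-L1 expression to allow for estimation of clinical activity in each subgroup". It then adds a third arm of participants who progressed on prior PD-1/PD-L1 therapy.

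**The concern.** All three arms receive the same triplet, so a definition based on drug and dose cannot separate them. A programmer who applies it as written would produce one Kaplan-Meier curve each for DR, PFS and OS, and one BOR table, over about 60 participants from three populations.

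Section 2.2.2 sets up the two naive arms because activity may be enriched at high PD-L1. The third arm differs from them in prior therapy. Table 3 lists DR, TTR, PFS and OS as the Phase 2 secondary measures of anti-tumour activity. If the arms differ, a combined median reflects the 20/20/20 enrolment mix and cannot be compared with expectations for either the first-line or the post-PD-1 setting. DR and TTR would also be weighted towards whichever arm has the most responders.

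**Working it through.** **1. The plan's own design figure.** Section 5.1.1.2 sizes each arm at 20 to give a standard error of ORR of at most 0.11. With SE = √(p(1−p)/n), p = 0.5 and n = 20, SE = √(0.25/20) = 0.1118, which is 0.11 to two decimals. The stated precision is therefore per arm. A single group of 60 would have SE = √(0.25/60) = 0.0645.

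**2. Which grouping applies to each Sub-Study B Phase 2 output.**

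| Output | Section | Grouping stated |
|---|---|---|
| Primary ORR | 6.1.2.2.1 | Arms B1, B2, B3 and overall |
| BOR categories, tumour shrinkage | 6.2.2.1, 6.2.2.2 | Treatment group |
| DR, PFS | 6.2.2.3, 6.2.2.5 | Treatment group |
| TTR | 6.2.2.4 | None of its own; the 6.2.2 rule applies |
| OS | 6.2.2.6 | Sub-study and treatment group |

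**3. Whether another section fills the gap.** Section 6.2.5 adds BOR by PD-L1 status. The pretreated arm also requires TPS of at least 1%, so PD-L1 status does not separate naive from pretreated participants. Section 6.4 says OR and durable OR "will be summarized in the following subsets within each treatment group"; the subsets are region, age, gender, race and ECOG PS, without arm or prior therapy. No section gives DR, TTR, PFS or OS by arm.

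**4. How much a combined figure could mislead.** The SAP gives no expected PFS medians, so the medians below are assumptions. With exponential PFS and equal arms, the pooled curve is S(t) = (1/3) Σ 2^(−t/mᵢ), where mᵢ are the arm medians. The pooled median solves S(t) = 0.5.

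| Assumed medians, months (naive, naive, pretreated) | Pooled median | 12-month PFS by arm | Pooled 12-month PFS |
|---|---|---|---|
| 8, 12, 3 | 6.4 | 35%, 50%, 6% | 31% |
| 6, 10, 2.5 | 5.1 | 25%, 44%, 4% | 24% |
| 6, 8, 4 | 5.7 | 25%, 35%, 12.5% | 24% |
| 8, 8, 8 | 8.0 | 35% in each | 35% |

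Check of the first row at t = 6.35: (0.577 + 0.693 + 0.231)/3 = 0.50.

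In the first two rows the pooled median is about twice the pretreated median (6.35/3 = 2.1; 5.1/2.5 = 2.0). It is 21% and 15% below the lower naive median. In the third row it is 1.4 times the pretreated median (5.7/4) and only 5% below the lower naive one. With equal arms nothing is distorted.

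**The case against.** A reader might infer that the SAP has decided to pool the three arms. The text does not go that far. No sentence orders pooling, and the single Phase 2 entry is a placeholder for a dose not yet known. In Section 3.4.1 the arms follow directly after the list and could be taken as subdividing it. Section 2.2.2 calls them treatment arms. In Section 6.2.6, ADA and NAb categories are summarised by treatment arm and overall, while ADA and NAb incidence is summarised by treatment group and overall, which suggests the terms may be interchangeable.

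This makes the intent uncertain but does not settle it. Section 5.2 repeats the list without the arms, and Section 6.1.2.2.1 names the arms explicitly when it wants them, so a literal reader has good grounds to combine.

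Two further points stand. CR plus PR is already available by arm through the primary ORR, so for BOR only the category breakdown is affected. And Sub-Study B Phase 2 has no hypothesis test, decision rule or interim analysis. Arm membership rests on baseline data, and Section 2 allows additional analyses, so by-arm tables could still be added before reporting.

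**Conclusion.** The point holds as a wording fault with analytical consequences. Applied literally, the definition of treatment group combines treatment-naive and PD-1/PD-L1-pretreated participants in every Sub-Study B Phase 2 output of Section 6.2.2, against the purpose of the arms in Section 2.2.2.

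Its size cannot be taken from the SAP. Under the assumed medians it ranges from none (equal arms), through small (6, 8, 4), to a pooled median about twice that of the pretreated arm (8, 12, 3 and 6, 10, 2.5). A reader might infer that the pooled figure must always lie far from every arm. The 6, 8, 4 case shows otherwise.

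A reader might also infer that the primary result is compromised. It is not: ORR is explicitly presented by arm. The outputs affected are descriptive secondary ones, so this is a should-fix.

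**What to change.** First, reconcile the arm definitions. Section 2.2.2 has B1 as TPS 1–49% and B2 as TPS ≥50%. Section 3.4.1 reverses these, labels the pretreated arm B2 a second time, and defines it only by prior advanced or metastatic therapy, whereas Section 2.2.2 requires progression on prior PD-1/PD-L1 therapy. Adding by-arm outputs before this is settled could attach results to the wrong population.

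Then add one sentence to Sections 5.2 and 6.2.2: all Sub-Study B Phase 2 efficacy outputs in Section 6.2.2 (BOR, tumour shrinkage, DR, TTR, PFS, OS) are presented by arm B1, B2 and B3, and any overall column is labelled descriptive.

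Leave the study-treatment definition in Section 3.4.1 unchanged. It is the same defined term as treatment group, so splitting it by population would also alter the safety, PK and exposure groupings.

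The cost is a sentence in each section and extra table columns. Intervals will be wide at 20 per arm (worst-case SE of a proportion 0.112, against 0.065 for 60), which the plan already accepts for ORR. Settling the wording before database release avoids choosing the grouping after results are visible in an open-label study.

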6.2.2.1. Objective response as assessed by the Investigator per RECIST v1.1

Best overall response (BOR) will be assessed based on reported overall lesion responses at different evaluation time points from the date of first dose of study treatment until the first documentation of PD, according to the following rules. Only tumor assessments performed on or before the start date of any further anti-cancer therapies will be considered in the assessment of BOR. Clinical deterioration will not be considered as documentation of disease progression.

BOR Based on Confirmed Responses:

- CR = at least two determinations of CR at least 4 weeks apart and before first documentation of PD
- PR = at least two determinations of PR or better (PR followed by PR or PR followed by CR) at least 4 weeks apart and before first documentation of PD (and not qualifying for a CR)
- SD (applicable only to participants with measurable disease at baseline) = at least one SD assessment (or better) ≥ 6 weeks after the date of first dose of study treatment and before first documentation of PD (and not qualifying for CR or PR).
- Non-CR/non-PD (applicable only to participants with non-measurable disease at baseline) = at least one non-CR/non-PD assessment (or better) ≥ 6 weeks after the date of first dose of study treatment and before first documentation of PD (and not qualifying for CR or PR).
- PD = first documentation of PD ≤ 12 weeks after the date of first dose of study treatment (and not qualifying for CR, PR, SD or non-CR/non-PD).
- NE: all other cases.

An objective status of PR or SD cannot follow one of CR. SD can follow PR only in the rare case that tumor increases by less than 20% from the nadir, but enough that a previously documented 30% decrease from baseline no longer holds. If this occurs, the sequence PR-SD-PR is considered a confirmed PR. A sequence of PR – SD – SD – PD would be a best response of SD if the window for SD definition has been met.

Objective Response (OR) is defined as confirmed BOR of CR or PR according to RECIST v1.1.

Participants who do not have a post-baseline radiographic tumor assessment due to early progression, who receive anti-cancer therapies other than the study treatments prior to reaching a CR or PR, or who die, progress, or drop out for any reason prior to reaching a CR or PR will be counted as non-responders in the assessment of OR. Each participant will have an objective response status (0: no OR; 1: OR). OR rate (ORR) is the proportion of participants with OR in the analysis set.

ORR by treatment group will also be calculated along with the 2-sided 95% CI using the Clopper-Pearson method³ (exact CI for a binomial proportion as computed by default by the FREQ procedure using the EXACT option).

In addition, the frequency (number and percentage) of participants with a confirmed BOR of CR, PR, SD, non-CR/non-PD (applicable only to participants with non-measurable disease at baseline), PD, and NE will be tabulated. Participants with confirmed BOR of NE will be summarized by reason for having NE status. The following reasons will be used:

- No baseline assessment
- No post-baseline assessments due to death
- No post-baseline assessments due to other reasons
- All post-baseline assessments have overall response NE
- New anti-cancer therapy started before first post-baseline assessment
- SD of insufficient duration (<6 weeks after the date of first dose of study treatment without further evaluable tumor assessments)
- PD too late (>12 weeks after the date of first dose of study treatment)

Special and rare cases where BOR is NE due to both SD of insufficient duration and late PD will be classified as ‘SD too early’ (i.e., SD of insufficient duration).

6.2.2.2. Tumor shrinkage from baseline

Tumor shrinkage will be summarized as the percent change from baseline in target lesions (sum of longest diameter for non-nodal lesion and short axis for nodal lesion) per time point.

It will be derived as:

- $((\text{Sum of target lesions at week XX} - \text{sum of target lesions at baseline}) / \text{sum of target lesions at baseline}) \times 100$

The maximum reduction in target lesions from baseline will be derived across all the post-baseline assessments until documented disease progression, excluding assessments after start of subsequent anti-cancer therapy, as:

- $\text{Minimum of } ((\text{sum of target lesions at week XX} - \text{sum of target lesions at baseline}) / \text{sum of target lesions at baseline}) \times 100$

A waterfall plot of maximum percent reduction in the sum of longest diameter for non-nodal lesions and short axis for nodal lesions from baseline will be created by treatment group.

These plots will display the best percentage change from baseline in the sum of the diameters of all target lesions for each participant with measurable disease at baseline and at least one post-baseline assessment.

6.2.2.3. Duration of response

Duration of Response (DR) is defined, for participants with OR, as the time from the first documentation of objective response (CR or PR) to the date of first documentation of PD or death due to any cause. If a participant has not had an event (PD or death), DR is censored at the date of last adequate tumor assessment. The censoring rules for DR are described in Table 9.

$$\text{DR (months)} = [\text{date of event or censoring} - \text{first date of OR} + 1] / 30.4375$$

Table 9. Outcome and Event Dates for DR Analyses

Scenario	Date of event/censoring	Outcome
PD or death - After at most one missing or inadequate post-baseline tumor assessment, OR - ≤ 16 weeks after the date of first dose of study treatment	Date of PD or death	Event
PD or death - After 2 or more missing or inadequate post-baseline tumor assessments	Date of last adequate tumor assessment ^a documenting no PD before new anti-cancer therapy is given or missed tumor assessments	Censored
No PD and no death	Date of last adequate tumor assessment ^a documenting no PD before new anti-cancer therapy is given or missed tumor assessments	Censored
Treatment discontinuation due to ‘Disease progression’ without documented progression	Not applicable	Information is ignored. Outcome is derived based on documented progression only.
New anti-cancer therapy given	Date of last adequate tumor assessment ^a documenting no PD before new anti-cancer therapy is given or missed tumor assessments	Censored

^a If there are no adequate post-baseline assessments prior to PD or death, then the time without adequate assessment should be measured from the date of first dose of study treatment; if the criteria were met the censoring will be on the date of first dose of study treatment.

Kaplan-Meier estimates (product-limit estimates) will be presented by treatment group together with a summary of associated statistics including the median DR time with 2-sided 95% CIs. In particular, the DR rates at 6, 10, 12, 15, 18, and 24 months will be estimated with corresponding 2-sided 95% CIs. The CIs for the median will be calculated according to Brookmeyer and Crowley (1982)² and the CIs for the survival function estimates at the time points defined above will be derived using the log-log transformation according to Kalbfleisch and Prentice (2002)⁶ (conftype=loglog default option in SAS Proc LIFETEST)

with back transformation to a CI on the untransformed scale. The estimate of the standard error will be computed using Greenwood’s formula.

DR will be displayed graphically and analyzed using Kaplan-Meier methodology. If the number of participants with OR is small, the Kaplan-Meier method may not provide reliable estimates. In this case, only descriptive statistics or listings will be provided.

Frequency (number and percentage) of participants with each event type (PD or death) and censoring reasons will be presented by treatment group. Reasons for censoring will be summarized according to the categories in Table 10 following the hierarchy shown.

Table 10. DR Censoring Reasons and Hierarchy

Hierarchy	Condition	Censoring Reason
1	Start of new anti-cancer therapy	Start of new anti-cancer therapy
2	Event after 2 or more missing or inadequate post-baseline tumor assessments	Event after 2 or more missing assessments ^a
3	No event and [withdrawal of consent date ≥ date of randomization OR End of study (EOS) = Participant refused further follow-up]	Withdrawal of consent
4	No event and lost to follow-up in any disposition page	Lost to follow-up
5	No event and [EOS present OR disposition page for any epoch after screening says participant will not continue into any subsequent phase of the study] and no adequate post-baseline tumor assessment	No adequate post-baseline tumor assessment
6	No event and none of the conditions in the prior hierarchy are met	Ongoing without an event

^a 2 or more missing or inadequate post-baseline tumor assessments.

